- Common fruits and vegetables are listed in the POW-R magazine on page 3.

How are fruits and vegetables good for you? (page 4)

- Research has shown that eating fruits and vegetables can help you live longer. Eating fruits and vegetables reduces the risk of getting some cancers, high blood pressure (hypertension), heart disease, and diabetes.
- Fruits and vegetables have all of these great health benefits because they have a lot of vitamins C and A, electrolytes, and antioxidants. Vitamin C protects cells and molecules from damage that causes many diseases, including cancer.
- Fruits and vegetables are also a great source of fiber. The fiber in fruits and vegetables lowers cholesterol, which reduces heart disease risk. The fiber in fruits and vegetables can also help control the body's blood sugar, which reduces risk of diabetes. Fruits and vegetables can also help you have a healthy weight by giving you lots of fiber and water, which can fill you up without giving too many calories.

If YES: Okay great, I'm glad you got a chance to review the material. Just to make sure that the magazine clearly conveyed the information, I will now ask you some questions to go over the main points of the magazine. We will then work together to create your personal action plan to eat more power vegetables. Before we begin, please pull out the packet we sent. It would really help to have them with you for the later part of the call. Please have a pen handy too (Go to PART D).

If NO: That is okay. We can still go over what is in the packet right now. Before we begin, please pull out the packet we sent. It would really help to have them with you for the later part of the call. Please have a pen handy too. (Go to PART B)

Part D: Going over Magazine Components: Teach Back

Just to make sure that the magazine clearly conveyed the information, I am now going to ask you a few questions to review some of the main points of the magazine. You may feel like I'm testing you, but the purpose of this is to make sure that the magazine communicated the information to you clearly. Are you ready? Let's go!

Note: For a question to be answered correctly, all parts of the question must be answered correctly.

CTB1 How are fruits and vegetables good for you?

Correct: 1) have lots of vitamins that 2) reduces the risk of getting some cancers, high blood pressure (hypertension), heart disease, and diabetes, 3) fiber in fruits and vegetables can also help you have a healthy weight

		Correct
No	Yes	

CORRECT: Yes, that's right!

INCORRECT: Let's go to page X in the POW-R Health magazine. On this page, there is a description of fruits and vegetables are good for you. Fruits and vegetables are good for you because they 1) have lots of vitamins that 2) reduces the risk of getting some cancers, high blood pressure (hypertension), heart disease, and diabetes, 3) fiber in fruits and vegetables can also help you have a healthy weight.

CTB2 How many cups of fruit do you need to eat each day?

Correct Answer: 1 ½ to 2 cups/day

Correct
No Yes

CORRECT: Yes, that's right- good job!

INCORRECT: If you look at on page X of your POW-R Health Magazine, there is the recommendation on how many cups of fruit to each day for best health. For best health, you need to eat 1 ½ to 2 cups of fruit a day. 1 cup of fruit is about the size of your fist.

CTB3 How cups of vegetables do you need to eat each day?

Correct Answer: 2 ½ to 3 cups/day

Correct
No Yes

CORRECT: Excellent, you're right.

INCORRECT: If you look at on page X of your POW-R Health Magazine, there is the recommendation on how many cups of vegetables to each day for best health. For best health, you need to eat 2 ½ to 3 cups of vegetables a day. 1 cup of vegetables is about the size of your fist.

CTB4 What does 1 cup of fruit or vegetable look like?

Correct Answer: 1 cup is about the size of your fist.

Correct
No Yes

CORRECT: Excellent, you're right. 1 cup of vegetables or fruit is about the size of your fist.

INCORRECT: If you look at on page X of your POW-R Health Magazine, there are pictures of what 1 cup looks like. The size of your fist is about 1 cup.

CTB5 Fresh, frozen, and canned fruits can all be a part of healthy eating. Can you please tell me what you need to watch out for when you buy canned fruit?

Correct Answer: Added sugars in canned fruit (buy no added sugar, 100% fruit juice kind)

Correct
No Yes

CORRECT: Ok great, you're right.

INCORRECT: If you look at on page X of your POW-R Health Magazine, there is describes what types of fruit are best to eat. Fresh, frozen, and canned fruits can all be a part of healthy eating. When it comes to canned fruits, you just need to watch out for too much sugar. Buy the no added sugar type.

CTB6 Fresh, frozen, and canned vegetables can all be a part of healthy eating. Can you please tell me what you need to watch out for when you buy canned vegetables

*Correct Answer: Too much salt in canned vegetables
(buy no salt added kind)*

Correct
No Yes

CORRECT: Ok great, you're right.

INCORRECT: If you look at on page X of your POW-R Health Magazine, there is describes what types of vegetables are best to eat. Fresh, frozen, and canned vegetables can all be a part of healthy eating. When it comes to canned vegetables, you just need to watch out for too much salt. Buy the no salt added.

CTB7 Can fruit juices be a part of a healthy diet?

Correct Answer: It's best to choose fruits you can eat instead of drink. Many fruit juices are high in sugar and calories and don't have a lot of minerals that fruit has when you eat them instead.

Correct
No Yes

CORRECT: Yes, that's right- good job!

INCORRECT: If you look at on page X of your POW-R Health Magazine, there it talks about fruit juices. It's best to choose fruits you can eat instead of drink. Many fruit juices are high in sugar and calories and don't have a lot of minerals that fruit has when you eat them instead.

Scoring Circle all questions that were answered incorrectly.

none	TB1	TB2	# Incorrect
TB3	TB4	TB5	
TB6	TB7		

ALL CORRECT: Excellent job! You really read through the POW-R Health Magazine and you got all of those questions correct. Now let's move on and put together an Action Plan! *[Go to Part F]*

ANY INCORRECT: *[GO TO PART E]*

Part E: Going over Magazine Components: Teach Back Opportunity

Only ask questions that were answered incorrectly in Part D. SKIP if all questions were answered correctly in Part D.

Is this part applicable?

No Yes

You did a good job remembering information that I just covered. I know there was a lot of information covered. So, let's just briefly recap the ones you missed.

CTB1.2 How are fruits and vegetables good for you?

Correct: 1) have lots of vitamins that 2) reduces the risk of getting some cancers, high blood pressure (hypertension), heart disease, and diabetes, 3) fiber in fruits and vegetables can also help you have a healthy weight

Correct

No Yes

CORRECT: Yes, that's right!

INCORRECT: Let's go to page X in the POW-R Health magazine. On this page, there is a description of fruits and vegetables are good for you. Fruits and vegetables are good for you because they 1) have lots of vitamins that 2) reduces the risk of getting some cancers, high blood pressure (hypertension), heart disease, and diabetes, 3) fiber in fruits and vegetables can also help you have a healthy weight.

CTB2.2 How many cups of fruit do you need to eat each day?

Correct Answer: 1 1/2 to 2 cups/day

Correct

No Yes

CORRECT: Yes, that's right- good job!

INCORRECT: If you look at on page X of your POW-R Health Magazine, there is the recommendation on how many cups of fruit to each day for best health. For best health, you need to eat 1 1/2 to 2 cups of fruit a day. 1 cup of fruit is about the size of your fist.

CTB3.2 How cups of vegetables do you need to eat each day?

Correct Answer: 2 1/2 to 3 cups/day

Correct

No Yes

CORRECT: Excellent, you're right.

INCORRECT: If you look at on page X of your POW-R Health Magazine, there is the recommendation on how many cups of vegetables to each day for best health. For best health, you need to eat 2 1/2 to 3 cups of vegetables a day. 1 cup of vegetables is about the size of your fist.

CTB4.2 What does 1 cup of fruit or vegetable look like?

Correct Answer: 1 cup is about the size of your fist.

Correct

No

Yes

CORRECT: Excellent, you're right. 1 cup of vegetables or fruit is about the size of your fist.

INCORRECT: If you look at on page X of your POW-R Health Magazine, there are pictures of what 1 cup looks like. The size of your fist is about 1 cup.

CTB5.2 Fresh, frozen, and canned fruits can all be a part of healthy eating. Can you please tell me what you need to watch out for when you buy canned fruit?

Correct Answer: Added sugars in canned fruit (buy no added sugar, 100% fruit juice kind)

Correct

No

Yes

CORRECT: Ok great, you're right.

INCORRECT: If you look at on page X of your POW-R Health Magazine, there is describes what types of fruit are best to eat. Fresh, frozen, and canned fruits can all be a part of healthy eating. When it comes to canned fruits, you just need to watch out for too much sugar. Buy the no added sugar type.

CTB6.2 Fresh, frozen, and canned vegetables can all be a part of healthy eating. Can you please tell me what you need to watch out for when you buy canned vegetables

Correct Answer: Too much salt in canned vegetables (buy no salt added kind)

Correct

No

Yes

CORRECT: Ok great, you're right.

INCORRECT: If you look at on page X of your POW-R Health Magazine, there is describes what types of vegetables are best to eat. Fresh, frozen, and canned vegetables can all be a part of healthy eating. When it comes to canned vegetables, you just need to watch out for too much salt. Buy the no salt added.

CTB7.2 Can fruit juices be a part of a healthy diet?

Correct Answer: It's best to choose fruits you can eat instead of drink. Many fruit juices are high in sugar and calories and don't have a lot of minerals that fruit has when you eat them instead.

Correct

No

Yes

CORRECT: Yes, that's right- good job!

INCORRECT: If you look at on page X of your POW-R Health Magazine, there it talks about fruit juices. It's best to choose fruits you can eat instead of drink. Many fruit juices are high in sugar and calories and don't have a lot of minerals that fruit has when you eat them instead.

Scoring Circle all questions that were answered incorrectly.
g

non	TB1	TB2	# Incorrect
e	TB4	TB5	
TB3	TB7		
TB6			

ALL CORRECT: Excellent job! You really read through the POW-R Health Magazine and you got all of those questions correct. Now let's move on and put together an Action Plan! *[Go to Part F]*

ANY INCORRECT: We'll go over these questions one more time before we end our call today. *[GO TO PART F]*

Part F: Complete Action Plan with Participant

Now let's go to the Action plan, which is on page 9 of the POW-R Health Magazine. Write your answers down in the plan.

Reasons for joining the POW-R Health Program

What are the most important reasons you have for joining the POW-R Health Program? Write this/these down in your action plan.

Participant reason(s):

Power vegetable eating goals

Let's set some short- and long-term goals. Let's start with a long-term goal. In 6 months, which is by the end of this program, how many cups of fruit and vegetables do you pledge to eat each day.

Long term goal

Now let's set your short-term goal. For this week, how many cups of fruit and vegetables will you try to eat this week?

Short-term goal

Who can help me

Who can help you eat more fruit and vegetables?
Who can support you?

Support person

Fruit and vegetable obstacles and strategies

Let's now talk about some obstacles that could make it harder for you to complete your plan. What are one or two obstacles that could make it harder for you to eat more fruit and vegetables every day?

Obstacle 1

Obstacle 2

What are some strategies you could use to help overcome the obstacles you listed?

Obstacle 1, Strategies (2-4)

Obstacle 2, Strategies (2-4)

My plan this week to eat more fruit and vegetables

Now let's make a plan to eat more fruit and vegetables this week. The next time you or someone else goes to the grocery store, which fruit and vegetables will you buy?

Fruit and vegetables to buy

Part G: Go over POW-R Track Book

One of the things you received in the packet we mailed to you is a POW-R Book. Please have your POW-R Book ready to review. In this book, I am asking that you keep track of how many fruit and vegetables you eat every day, and each week. Science shows that keeping track of what you eat is a powerful way to change your habits. Keeping track of how many fruit and vegetables you eat will help you eat more fruit and vegetables. Let's go over all of the parts of the POW-R Book.

Check box when section is covered

1. 1 POW-R book for each week; 24 sent to you—1 is for practice to use now; we are asking you to complete a track book each week for the entire program	3. 7 days in one POW-R book	5. Each day write down how many cups of fruit you had that day. (have them go through pages of book)	7. On the back is the phone number of the person from our team that you can call
---	-----------------------------	--	--

2. Cover page—write down dates of the week you are keeping track

4. Each day write down how many cups of vegetables you had that day. (have them open up book)

6. On the front page, is where you will write down: 1) the total cups of fruit, 2) total cups of vegetables, and 3) total number of fruits AND vegetables you ate that week. Place a check-mark by whether you ate at least 1.5 cups of fruit that week (yes/no). Same with vegetables. After our phone call, you will receive automated messages and will be asked to enter the total number of cups of fruit AND vegetables you ate for the week (refer them to last line). It will also ask you whether you ate at least 1.5 cups of fruit, and 2.5 cups of vegetables and you will use the information here to tell them 'yes' or 'no'

if you have any questions.

8. Any questions?

Let's practice using the POW-R Track Book.

Practice using POW-R Track Book

Take a POW-R Track Book. Can you think back this past week of any fruit you ate? Let's go through each day.

Now let's add how many cups you ate that week

	Monday	Tuesday	Wed	
	Thursday	Friday	Sat	Sunday
	Total			Correct
				No Yes

CORRECT: Yes, that's right- good job!

INCORRECT: Ok, so the correct total is X. Let's try that again to make sure you can use the POW-R Book correctly. Feel free to use a calculator if that would make things easier.

Part H: Going over magazine components: Teach Back Opportunity #3

Only ask questions that were answered incorrectly in Part E. SKIP if all questions were answered correctly in Part D or E.

Is this Part applicable?

No Yes

Before we end the call, I just want to re-ask you the questions about the key points from the magazine that you were not able to recall last time

CTB1.3 How are fruits and vegetables good for you?

Correct: 1) have lots of vitamins that 2) reduces the risk of getting some cancers, high blood pressure (hypertension), heart disease, and

Correct
No Yes

*diabetes, 3) fiber in
fruits and vegetables
can also help you
have a healthy weight*

CORRECT: Yes, that's right!

INCORRECT: Let's go to page X in the POW-R Health magazine. On this page, there is a description of fruits and vegetables are good for you. Fruits and vegetables are good for you because they 1) have lots of vitamins that 2) reduces the risk of getting some cancers, high blood pressure (hypertension), heart disease, and diabetes, 3) fiber in fruits and vegetables can also help you have a healthy weight.

CTB2.3 How many cups of fruit do you need to eat each day?

Correct Answer: 1 ½ to 2 cups/day

Correct

No

Yes

CORRECT: Yes, that's right- good job!

INCORRECT: If you look at on page X of your POW-R Health Magazine, there is the recommendation on how many cups of fruit to each day for best health. For best health, you need to eat 1 ½ to 2 cups of fruit a day. 1 cup of fruit is about the size of your fist.

CTB3.3 How cups of vegetables do you need to eat each day?

Correct Answer: 2 ½ to 3 cups/day

Correct

No

Yes

CORRECT: Excellent, you're right.

INCORRECT: If you look at on page X of your POW-R Health Magazine, there is the recommendation on how many cups of vegetables to each day for best health. For best health, you need to eat 2 ½ to 3 cups of vegetables a day. 1 cup of vegetables is about the size of your fist.

CTB4.3 What does 1 cup of fruit or vegetable look like?

Correct Answer: 1 cup is about the size of your fist.

Correct

No

Yes

CORRECT: Excellent, you're right. 1 cup of vegetables or fruit is about the size of your fist.

INCORRECT: If you look at on page X of your POW-R Health Magazine, there are pictures of what 1 cup looks like. The size of your fist is about 1 cup.

CTB5.3	Fresh, frozen, and canned fruits can all be a part of healthy eating. Can you please tell me what you need to watch out for when you buy canned fruit?	Correct
		No Yes

Correct Answer: Added sugars in canned fruit (buy no added sugar, 100% fruit juice kind)

CORRECT: Ok great, you're right.

INCORRECT: If you look at on page X of your POW-R Health Magazine, there is describes what types of fruit are best to eat. Fresh, frozen, and canned fruits can all be a part of healthy eating. When it comes to canned fruits, you just need to watch out for too much sugar. Buy the no added sugar type.

CTB6.3	Fresh, frozen, and canned vegetables can all be a part of healthy eating. Can you please tell me what you need to watch out for when you buy canned vegetables	Correct
		No Yes

Correct Answer: Too much salt in canned vegetables (buy no salt added kind)

CORRECT: Ok great, you're right.

INCORRECT: If you look at on page X of your POW-R Health Magazine, there is describes what types of vegetables are best to eat. Fresh, frozen, and canned vegetables can all be a part of healthy eating. When it comes to canned vegetables, you just need to watch out for too much salt. Buy the no salt added.

CTB7.3	Can fruit juices be a part of a healthy diet?	Correct
		No Yes

Correct Answer: It's best to choose fruits you can eat instead of drink. Many fruit juices are high in sugar and calories and don't have a lot of minerals that fruit has when you eat them instead.

CORRECT: Yes, that's right- good job!

INCORRECT: If you look at on page X of your POW-R Health Magazine, there it talks about fruit juices. It's best to choose fruits you can eat instead of drink. Many fruit juices are high in sugar and calories and don't have a lot of minerals that fruit has when you eat them instead.

Scoring	Circle all questions that were answered incorrectly .	none	TB1	TB2	# Incorrect
		TB3	TB4	TB5	
		TB6	TB7		

ALL CORRECT: Excellent job! You know all the important parts of the POW-R Health Magazine and you got all of those questions correct.

ANY INCORRECT: You did a good job remembering information from the magazine. I know there was a lot of information covered. So, let's just briefly recap the ones you missed before ending the call.

PART I: Closing

Thanks for taking the time to complete this call. Next week you will start receiving automated phone calls from our POW-R Health Program. The purpose of the calls will be to support you to eat more fruit and vegetables. The calls will be tailored personally to you. Each call will ask you how many fruit and vegetables you ate for the week, figure out whether you are meeting your action plan goals, and then give you tailored support based on the obstacles and strategies you wrote down in your action plan. So, it will really be important for you to complete your POW-R Book every day, calculate your total cups of fruit and vegetables eaten at the end of every week, and have that available when you receive the phone call.

The system will call you from this number: [name]. You can also call this number if you miss the call. This number is on the magnet we mailed to you to remind you that this is not a spam number. Can you please get the magnet we sent you out? Please place this magnet in a place that you'll be able to see it. If you miss a call, you can also call this number too to complete your automated phone call. There will be 11 automated phone call and we ask you to complete all 11 calls.

Each call will start by asking you what your date of birth is, so the system will know it is you. For example, if you were born January 3, 1953, you would enter 01-03-1953. The system will call you from this number: [name]. You can also call this number if you miss the call.

Can you tell me how you will enter your date of birth? *[Confirm that the participant can provide their DOB correctly]*

DOB	Correctly read
No	Yes

Each automated phone call will last about 10-15 minutes. Please stay on the phone until the call is complete, otherwise the system will think that you did not complete the call and it will call you again.

(Go over any magazine content questions they missed: Let's go over one last time the question(s) you missed)

What questions do you have for me before we hang up?

Record questions

Okay, just remember, if you ever have any questions or concerns, you can always get ahold of us by calling one of our team members at [contact], [name]. This number is on the back of the Track Book and the last page of the magazine.

Thank you for completing the call!

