
Control intervention. Participants in the control arm will receive mailed materials about general fruit and vegetable intake intervention based on published NCI guidelines. (<https://cancercontrol.cancer.gov/ocs/>). The control intervention will utilize the same delivery method (i.e. mailed educational materials, live phone call, IVR calls) and follow the same contact schedule as the treatment schedule (See Appendix P and Appendix Q). We intend to compare our tailored cruciferae program with general program on increase of fruit and vegetable intake. We anticipate minimal contamination between intervention and control because BCS will be recruited throughout our catchment area and our intervention will be delivered individually with each BCS.

Personnel Training. [name] will utilize her extensive experience in training others in the delivery of behavioral interventions to train project staff to implement the intervention. A training-of-trainers model that incorporates didactic education, trainee practice, and written and verbal feedback will be used. Training will build knowledge about behavior change promotion, with a specific emphasis on delivering the live phone call with fidelity, utilizing participant booklets to program the IVR messages, and communicating effectively with participants about health. The training will conclude with project staff demonstrating mastery of concepts through mock phone sessions and live phone calls, and accurate programming based on booklet data received. Project staff will be asked to complete a checklist of topics to monitor intervention fidelity.

Aim 2: Conduct a feasibility pilot of our evidence-based dietary behavioral intervention

Study Design. We will use a Hybrid I implementation randomized-controlled design to simultaneously gather outcomes regarding the intervention's feasibility and process data to facilitate wide-spread implementation and dissemination of the intervention into clinical practice if the intervention is effective. A total of 80 patients will be recruited on a rolling basis. Forty will be randomized to intervention and 40 to control.

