Whisk the olive oil, lemon juice, salt, and a few grinds of black pepper together in a large bowl. Add the arugula and toss to combine. Top with the shaved Parmesan and serve immediately.

RECIPE NOTES

Make ahead: The dressing can be made up to 5 days ahead of time and stored in an airtight container in the refrigerator. Rewhisk again before using.

Source: theadt.com

Can I take a
vitamin pill instead
of eating power
vegetables?

[figure not shown]
Vitamin pills don't
have the anti-cancer
isothiocyanates that
power vegetables
have. So, vitamin
pills can't replace
power vegetables.

POW-R HEALTH: Power to Redefine Your Health

3

18 POW-R HEALTH: Power to Redefine Your Health

Do I need to buy organic power vegetables or vegetables from a farmer's market?

No. Organic and farmer's market power vegetables don't have more isothiocyanates than power vegetables you can get from a grocery store.

What are power vegetables?

Power vegetables are **cruciferous vegetables**: a group of vegetables where the flowers on the vegetables form the shape of a cross (in Latin, *Cruciferae* means "cross bearing"). Power vegetables include:

- Broccoli
- Turnips
- Green or white cabbage
- Brussels sprouts
- Radishes
- Arugula
- Mustard greens, and
- Other vegetables listed below

Humans have eaten power vegetables for many years. But the anti-cancer parts of power vegetables were not known until lately. Power vegetables are rich in many vitamins and minerals, such as folate, vitamins C, E, and K, and are a good source of fiber. Best for cancer survivors, power vegetables have a group of unique things called glucosinolates. Glucosinolates give power vegetables their strong smell and bitter taste. When power vegetables are cooked and eaten, glucosinolates are broken down into some active things. One of these active things is isothiocyanates. Doctors have found that isothiocyanates have strong anti-cancer actions against many types of cancer, including bladder cancer.

Why are power vegetables good at fighting bladder cancer?

When we eat power vegetables, isothiocyanates go to the bladder through the urine and build-up in the urine. Bladder cancer cells mostly form on the inside surface of the bladder and are exposed to the urine. When the isothiocyanates builds up in the urine, bladder cancer cells get soaked in isothiocyanates that are in the urine. Being exposed to isothiocyanates in the urine help kill bladder cancer cells and stop them from growing.

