A1. Did you receive the program packet in the mail?

If YES: (Go to Question A2)

If NO: It's really important that you have your packet before we go over it. Let me make a note to send you the packet again. What is your mailing address? I'll call you again after your packet is sent. Thank you for taking the time to talk with me. I'll talk to you again soon.

END CALL.

A2. If so, did you have time to review the information in this packet?

No Yes

Mailing Address

No Yes

If YES: Okay great, I'm glad you got a chance to review the material. Just to make sure that the magazine clearly conveyed the information, I will now ask you some questions to go over the main points of the magazine. We will then work together to create your personal action plan to eat more power vegetables. Before we begin, please pull out the packet we sent. It would really help to have them with you for the later part of the call. Please have a pen handy too (Go to PART D).

If NO: That is okay. We can still go over what is in the packet right now. Before we begin, please pull out the packet we sent. It would really help to have them with you for the later part of the call. Please have a pen handy too. (Go to PART B)

PART B: OVERVIEW

I'm going to begin by going over the POW-R Magazine. After I go over the magazine's contents, we'll complete your personal action plan (page 12). I'll then go over the POW-R Books and the magnet. So, let's start with the POW-R Magazine. Please have your POW-R Magazine next to you so you can follow along what I'm going to review.

PART C: MAGAZINE CONTENT

Welcome to the POW-R Health Program (page 2)

- Among bladder cancer survivors like you, there is still a 50%-80% chance that the bladder cancer could come back within 5 years
- Compared to all types of cancers, bladder cancer has the highest chance of coming back
- If the cancer comes back and is not caught at early stages, there is a risk of losing the bladder
- Going to your routine check-ups with doctors is good to catch bladder cancer coming back at early stages. But they are not enough.
- Doctors made the **POW-R Health Program** to make sure you live the longest, healthiest life possible
- Certain vegetables that can help stop bladder cancer from coming back. These vegetables are called power vegetables
- Power vegetables help reduce death from bladder cancer by 57%

Interesting convo points

What are Power Vegetables? (page 4)

- Power vegetables are cruciferous vegetables

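### The control-arm live-call script retains the intervention arm's label, so controls who have read their packet are told their plan concerns power vegetables

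*Combined protocol and SAP*

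**What the plan says.** Section 11, under the control intervention, defines the comparator: "Participants in the control arm will receive mailed materials about general fruit and vegetable intake intervention based on published NCI guidelines". Delivery method and contact schedule match the treatment arm, so the arms are meant to differ in content only. The same paragraph states "We anticipate minimal contamination between intervention and control", and gives two reasons: recruitment is spread over the catchment area, and delivery is to one person at a time. Under personnel training, Section 11 stresses that the live call be delivered with fidelity, monitored by a topic checklist.

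In Appendix Q, the control script has a branch for participants who say they have reviewed the packet. It opens "Okay great, I'm glad you got a chance to review the material" and goes on to say "We will then work together to create your personal action plan to eat more power vegetables". Later in the control script, the goal-setting block in Part F is headed "Power vegetable eating goals". The prompt beneath that heading asks "how many cups of fruit and vegetables do you pledge to eat each day".

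The intervention script defines the label: "Power vegetables are cruciferous vegetables". The intervention magazine in Appendix P defines it the same way, as "a group of vegetables where the flowers on the vegetables form the shape of a cross". The readable text of the control magazine does not use the label. It lists cruciferous vegetables as one common type among several, and its action plan is for fruits and vegetables.

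**The concern.** The trial asks whether a cruciferae-specific programme does better than a general fruit-and-vegetable programme delivered in the same way. That comparison depends on controls receiving general content only. *Power vegetables* is not a neutral phrase here: it is the name the intervention arm gives to its target food group. A script that announces a power-vegetable plan to controls contradicts the definition of the control arm, the control magazine and the rest of the same call. Because staff are trained to deliver the call as written, good fidelity reproduces the error.

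What is at stake is the contrast between arms on the two primary outcomes. One of these, cruciferous intake, is self-reported by questionnaire and so is open to cueing.

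**Working it through.** The question is textual, so the passages are set side by side.

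1. **Is the sentence really in the control script?** The order of text in the control script is disturbed by extraction, so a misplaced fragment has to be ruled out. The intervention script has its own copy of the sentence in its packet-receipt section. The second copy follows the control magazine content and comes directly before the control-only teach-back questions. It belongs to the control script.

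2. **Who hears it?** Only controls who answer yes when asked whether they have reviewed the packet. The branch for those who answer no lacks the phrase. With 40 randomised to control, 40 is the upper bound. The documents give no expected share of yes answers.

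3. **What reaches them?**

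| Element | Intervention call | Control call |
|---|---|---|
| Label *power vegetables* | Yes, defined | Once in the yes branch, undefined; again in the Part F heading |
| Plan announced as | Power vegetables | Power vegetables (yes branch) |
| Plan actually completed | Power vegetables | Fruit and vegetables |
| ITCs, vegetable choice, light cooking, evening timing, one-serving goal | Yes | No |
| Teach-back, Track Book explanation, closing | Power vegetables | Fruit and vegetables |

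The label and the stated aim cross over. The working content does not.

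4. **Does the contamination argument cover it?** Geographic spread and individual delivery both limit contact between participants. Neither limits what study staff say to controls.

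5. **Does the sample size allow for it?** The plan's own figure reproduces. With 40 per arm, R² = 0.2 and two-sided alpha 0.05, the residual SD is √(1 − 0.2) = 0.894 of the outcome SD. Noncentral t with 77 df gives a detectable difference of 0.567 SD at 80% power, against the stated 0.57. Then 0.57 × 8.9 = 5.07 µM and 0.57 × 62 = 35.3 g/day, as stated. The calculation contains no allowance for contamination. The planned ITC rise is 10 − 4.4 = 5.6 µM against a detectable 5.1 µM, so if controls stay at baseline there is little slack.

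For orientation only: if something diluted a true 0.57 SD difference by 5% (to 0.5415 SD), power would be 76%; by 10% (to 0.513 SD), 72%. These percentages are assumptions. They show what any dilution would cost, and nothing in the documents ties this sentence to either value.

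**The case against.** The strongest defence is that what leaks is an undefined two-word label, heard once by some controls. Both arms carry the POW-R Health name and the control magazine's cover speaks of the health powers of fruits and vegetables, so a control could take the phrase as branding. The Part F heading is not shown to be read aloud, and the prompt below it is correct. Section 2 describes an earlier trial that raised vegetable intake without raising cruciferous intake or urinary ITC, and links ITC exposure to vegetable choice, cooking and timing. Controls get none of that guidance. Cueing adds little as well: before the programme, the baseline survey already asks everyone about many cruciferous vegetables by cooking method.

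All of this stands as a limit on the consequence. It gives no reason for controls to hear the sentence.

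Two stronger readings are tempting. A reader might infer that a control who asks what the phrase means must be told either the other arm's content or the hypothesis. That does not follow, because staff can correct themselves or point to the foods in the control magazine. A reader might also assign some share of controls the planned intake rise of 75 − 52.7 = 22.3 g/day and derive a loss in the between-arm difference. That rise is the target of the full six-month cruciferae programme. The documents do not support any share of controls reaching it from one undefined phrase.

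**Conclusion.** The point holds as an avoidable lapse in arm separation and script fidelity. The wording, its place in the control script and its conflict with the control definition are certain from the text. It matters more than a background typo because the sentence is spoken to participants by staff trained to follow the script, and the stated case for minimal contamination does not address it.

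The size is not known. Exposure is bounded by the 40 controls and limited to those who answer yes at the packet question. Given the absence of any definition, ITC content, preparation advice or serving goal, the effect on intake or urinary ITC is probably small. A material narrowing of the contrast on either primary outcome is not shown. This assumes that staff read the branch as written and add nothing about the term.

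**What to change.** In the control script of Appendix Q, change the sentence so that the action plan is to *eat more fruits and vegetables*, and retitle the Part F block *Fruit and vegetable eating goals*. This matches the control magazine and Section 11. Add a staff instruction not to use *power vegetables* with control participants.

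If control calls have already been made with the old text, record the date of the change and the number of such calls, and report both with the fidelity results. This is a live possibility: Sections 11 and 30 provide for cruciferous-arm participants who had completed follow-up by the March 2022 revision.

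The cost is two wording edits, a staff note and at most an appendix amendment. The small downside of a mid-trial change is that controls may have received two versions of the script, which is why the date and count should be kept.
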